# 8.7. Cardiac Assessments

- **8.7.1 12-lead ECG:** 12-lead ECG monitoring will be performed within 14 days before the start of treatment, at Cycle 1 Day 1 and Cycle 1 Day 5, and then at day 1 of all reinduction cycles and EOT.
  - C1D1: pre-dose, 2-hours post-dose morning dose and 2-hours post-dose evening dose
  - C1D5: 2-hours post-dose morning dose and 2-hours post-dose evening dose
  - **8.7.2.** Cardiac Imaging ECHO or MUGA:\_monitoring will be performed within 14 days before the start of treatment, and then prior to day 1 of each subsequent cycle if clinically indicated based on the treating physician's assessment.
  - **8.8. Pharmacokinetic Profile**: Blood samples for determination of plasma concentrations of CB-103, will be collected as detailed below:
  - C1D1: pre-dose, 2-, 6-hours post-dose morning dose and 2- hours post-dose evening dose (± 5 minutes)

Page | 32 04/25/2024

• C1D5: pre-dose, 2-, 6-hours post-dose morning dose and 2- hours post-dose evening dose (± 5 minutes)

On the day of PK sampling the patient should be fasting: on that day, CB-103 will be taken together with the study staff with a glass of water. On Cycle 1 Day 1 food should be withheld for at least 3 hours after study drug intake. Water can be taken ad libitum. On Day 5 of Cycle 1, food consumption can be started after the second PK sample.

**8.9. Laboratory assessments**: The following laboratory tests will be performed within 48 hours prior Day 1 of each cycle: they do not need to be repeated at Cycle 1, Day 1 if they were performed at screening within 48 hours prior to start of study treatment. They may be performed at a local laboratory. For table of assessment and schedule, see **Table 16**.

Outside labs will be permitted and the PI/treating physician will review the labs for clinical significance, and sign/date the results. If patients present treatment-related toxicities, monitor blood counts and chemistries as clinically indicated. These tests should include:

- **8.9.1.** Hematology: Complete blood counts (CBC), white blood count (WBC) with differential, unless WBC  $<0.5 \times 10^9$ /L (in which case differential not needed), hemoglobin, platelet count). Hematology assessments will be performed at least 2 times weekly during the first treatment cycle and at least 1 time weekly during each successive treatment cycle.
- 8.9.2. Coagulation: Prothrombin time (PTT) and activated partial thromboplastin time (aPTT)
- **8.9.3. Biochemistry**: Clinical Chemistry includes albumin, alkaline phosphatase, alanine aminotransferase (ALT), aspartate aminotransferase (AST), lactate dehydrogenase (LDH), carbon dioxide (CO2), uric acid, calcium, chloride, glucose, phosphorus, potassium, sodium, magnesium, total bilirubin, direct bilirubin (if total bilirubin is elevated above the upper limit normal), total protein, blood urea nitrogen (BUN) and creatinine. Clinical Chemistry will be performed at least 2 times weekly during the first treatment cycle and at least 1 time weekly during each successive treatment cycle.
- **8.9.4. Pharmacodynamic/Biomarker Assessments**: Serial blood, CSF, and bone marrow samples will be obtained if additional fluid is available to measure gene and protein expression levels of relevant pathways (e.g. NOTCH, BCL2) as well as for longitudinal monitoring of tumor evolution by NGS. Results will not be limiting for patient enrollment. The samples will be analyzed by Cellestia and/or their designated laboratory (ies) from the list below:
- Cellestia R&D (Switzerland)
- SGS (Switzerland)

Blood and bone marrow samples are mandatory at baseline for local evaluation. For all patients, repeated blood sampling and bone marrow biopsy will also be taken at completion of induction, reinduction cycles ± 3 days, and at time of progression. An additional blood sample to monitor target engagement (PD) will also be collected on C1D5 at one of the PK sampling timepoints and Day 26 of all cycles of treatment. Except for the baseline, blood samples must be taken on the last week-day of CB-103 intake before the 2 days off treatment.

Details on sample collection requirements, preparation, processing, storage, and shipment will be provided in a separate laboratorymanual.

Page | 33 04/25/2024

Changes to the sampling scheme may be implemented based on the emerging data. Any adjustment will be recorded in the study file and the total number of samples taken will not be exceeded.

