# **5.1.3.** Dosage and Administration.

CB-103 will be administered orally as 500 mg twice a day (BID) for 5 days on and 2 days off, which has now been declared the RP2D in adults (section 2.3.2 Clinical Studies), until disease progression per investigator's judgement, or until unmanageable drug related toxicity, or as long as the patients are continuing to derive clinical benefits (section 4.2 Treatment Plan). For patients already enrolled prior to Protocol Version 2.0, they will be reconsented and offered the increased dose if it is felt to be safe and in the patient's best interest by the treating physician, otherwise they may continue at their current dose of 500 mg daily.

Page | 15 04/25/2024

In the event of vomiting, no re-dosing will be provided. According to FDA recommendations, as for  $\geq$  12-year-old adolescent patients no weight-related clinically relevant effect on drug pharmacokinetics or safety are expected,  $\geq$  12-year-old adolescent patients enrolled in this trial may receive the same fixed daily dose as administered in adults (Clinical Growth Charts web page under National Center for Health Statistics at the Centers for Disease Control and Prevention website (https://www.cdc.gov/growthcharts/clinical\_charts.htm).

CB-103 will be provided as capsules of 100 mg each. Patients will be instructed to swallow the CB-103 capsules whole with a glass of water (approx. 200 mL) in the morning, on an empty stomach, at least one hour before taking breakfast; in the evening, within 8 to 12 hours of the first intake, at least one hour before the evening meal. Capsules should not be chewed prior to swallowing. Capsules that are broken, cracked, or otherwise damaged should not be ingested. In the exceptional case of a patient who is unable to swallow capsules, the capsules can be opened and the contents may be mixed in a spoon with a bit of yogurt or fruit puree in order to swallow and follow with a glass of approximately 200mL of water (IMP Manual).

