#### 7. CONCOMITANT THERAPY

Concomitant medication data will not be collected or entered into the case report form except for concomitant hydroxyurea and intrathecal chemotherapy; however, the subject's medication record will contain a list of concomitant medications. All supportive measures consistent with optimal patient care should be provided throughout the study according to the departmental standards.

- **7.1. Allowed Concomitant Therapy:** Prophylactic or therapeutic intrathecal therapy is allowed, if central nervous system leukemia involvement is diagnosed after enrollment in this clinical trial. The use of hematopoietic growth factors or transfusions is allowed. The use of hydroxyurea is permitted at any time during the study period for cytoreduction. Corticosteroids (e.g. for management of allergic reactions, prophylaxis, etc.) are also allowed. Use of other immunosuppressive therapy, e.g. tacrolimus, may be allowed at the disgression of the clinical provider. Other supportive care studies are allowed, even if under an IND.
- **7.2. Prohibited Concomitant Therapy:** Patients may not receive other investigational anti-neoplastic therapy drugs, excluding therapy as described in previous Section "Allowed Concomitant Therapy". Patients may not receive radiotherapy during the study.

The following medications should be strictly prohibited during the study treatment period, unless there are no signs of QTc prolongation in scheduled EKG:

- Drugs with a known risk to induce Torsades de Pointes: All QT-prolonging drugs (see Table 1 in of Appendix 1) are prohibited for all patients until permanent discontinuation of study treatment.
- Drugs with a conditional risk to induce Torsades de Pointes: Any QT prolonging medication with
  a conditional risk of inducing Torsades de Pointes listed in Table 2 of Appendix 1 are prohibited
  for all patients from screening through permanent discontinuation of study treatment, except for
  the assumptions described in Section 6.1.7. for the treatment of diarrhea and nausea. These
  exceptions must be discussed in advance with the Sponsor on a case-by-case basis.
- Warfarin and Coumarin-type anticoagulants within 1 week prior first CB-103 dose.

Page | 29 04/25/2024

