# 8. Visit schedule and study assessments

Written ICF for participation in the study must be obtained from the patient, signed and dated before performing any study procedure. Patients will be informed about the study drug and will receive pertinent information regarding the study objectives, possible benefits, and potential AEs. They will also receive information on the follow-up procedures and possible risks they will be exposed to. The ICF also informs patients about how biological samples will be obtained and collected and its legal implications. Patients are allowed to enter the study based on confirmation of the eligibility criteria (refer to inclusion and exclusion criteria in **Section 3.1.** and **Section 3.2.**) at screening/baseline.

Assessments scheduled for days 1 of each cycle must be performed within 48 hours prior to study treatment administration, unless otherwise indicated in the schedule of assessments, in order to confirm to the patient if treatment can continue. All examinations listed below will be performed according to the Schedule of Assessments outlined in **Table 16**.

All screening tests and evaluations must be completed and reviewed to confirm that patients meet all eligibility criteria within 21 days prior to the first administration of study medication. Disease assessments, such as bone marrow samples (aspirate and/or biopsy), EKG and LVEF evaluation, such as ECHO/MUGA scan, available and performed as part of clinical practice prior to obtain the signature of the ICF, and within 21 days prior to treatment start, are accepted. Therefore, such evaluations are not required to be repeated during the screening period.

Patients should be admitted for Cycle 1 days 1-7 to monitor for any adverse events and for completion of study evaluations due on day 5. Patients may be discharged after the completion of study evaluations at the discretion of the treating physician if drug combination is being tolerated without need for close monitoring for adverse events and patient is clinically stable for safe discharge.

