# 8. STUDY CALENDAR (28 day Cycle) Table 16: Study Calendar

	Screening		Treatment Period							End of Treatment Visit 	Follow- Up 		
		Cycle 1					Cycle 2			From Cycle 3			
Day of cycle	-21 to -1	1 	5	26	28	1 	26	28	1 	26	28	1	
Assessments 													
Informed Consent	Х												
Demographics with body height (cm)	Х												
Medical History	Х												
Disease history (including number of prior therapy regimens for ALL)	Х												
Inclusion/Exclusion	X												
ID Panel	X 												
Pregnancy Test	X 	X 				X 			X 			X 	
Vital Signs and body measurements													
ECOG Performance Status	X	Χ				X			Χ			X	X
Weight (kg)	Х	Χ				X			Χ			X	X
Physical Exam	Х	Χ		X 		Χ	X 3		Χ	X 		X	X
Eye examination (see Section 8.4)	X			Х			X			Х		X	X
Body Temperature	Х	Х				X			Χ			X	X
Respiratory rate	Х	Х				X			Χ			X	Х
Cardiac assessments													
Blood Pressure	Х	Х		Х		X	Х		Χ	Х		X	
12-Lead EKG	X 	Х	Х			Χ			Χ			X	
ECHO or MUGA	X 	X 				X			Χ			X	
Standard Laboratory Procedures													
Biochemistry 	Х	Χ	Х	Х		X	Х		Χ	Х			
Hematology 	Х	Х	Χ	Х		X	Х		Χ	Х			
Coagulation 	Х	Х	Х	Х		X	Х		Χ	Х			
Disease Assessment 	Х	X 		Х		X 	Х		X 	Х			X 
Pharmacokinetic profile 		Х	Х										
Biomarker Assessments 		Х	Х	Х			Х			Х		Х	
Lumbar puncture & CSF sampling 	Х			Х			Χ			Х			
Concomitant Medications	Х	Х	Х	Х		Χ	Х		X 	X 			
Adverse Events	Х	Х	Х	Х		Χ	Χ		Χ	Х		Х	Х
Survival Status				_									Х

Protocol 2021-0547 4/25/2024

- 1. Assessments scheduled on days of dosing should be done prior to administration of study drug(s), unless otherwise specified.
- 2. Screening assessments can be used as day 1 assessments of cycle 1 if done within the previous 72 hrs.
- 3. End of previous cycle assessments (Day 26) can be used as day 1 assessments if done within Day 26-29. If subsequent cycle is delayed, hematology, chemistry, and coagulation labs and physical exam assessments should be repeated on Day 1 of cycle.

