- 4. For women of childbearing potential only. Serum pregnancy test must be performed within 24-48 hours before first study treatment. During the on-treatment period and at the EoT visit, urine pregnancy testing should be done as indicated in the table or whenever a pregnancy is suspected. Pregnancy and suspected pregnancy occurring while the patient is on study drug treatment or within 90 days after the last dose of CB-103 should be reported to the supporting company (Cellestia AG).
- 5. Screening assessments can be used as day 1 assessments if done within the previous 14 days.
- 6. EKG and LVEF assessment by ECHO or MUGA should be done within 14 days before first study treatment: these assessments may be repeated at the Investigator's discretion in case of signs or symptoms of cardiotoxicity. See Sections 8.7.1 and 8.7.2.
- 7. Tests will be performed at least 2 times weekly during the first treatment cycle and at least 1 time weekly during each successive treatment cycle. Outside labs will be permitted and the PI/treating physician will review the labs for clinical significance, and sign/date the results. If patients present treatment-related toxicities, monitor blood counts and chemistries as clinically indicated. This assessment does not need to be repeated at Cycle 1, Day 1 if it was performed at screening within 48 hours prior to start of study treatment.
- 8. Laboratory tests to be performed locally, within 48 hours before study visit (Day 1 of each cycle, including Cycle 1, Day 1) include albumin, alkaline phosphatase, alanine aminotransferase (ALT), aspartate aminotransferase (AST), lactate dehydrogenase (LDH), carbon dioxide (CO2), uric acid, calcium, chloride, glucose, phosphorus, potassium, sodium, magnesium, total bilirubin, direct bilirubin (if total bilirubin is elevated above the upper limit normal), total protein, blood urea nitrogen (BUN) and creatinine.
- 9. CBC (WBC with differential, unless WBC <0.5 x109/L in which case differential not needed, Hemoglobin, and Platelet count).
- 10. Prothrombin time (PTT), activated partial thromboplastin time (aPTT), and fibrinogen. This assessment does not need to be repeated at Day 1 of cycles if it was performed within 3 days prior.
- 11. Disease assessment:
  - Bone marrow samples (aspirate and/or biopsy), cytogenetics, and flow cytometry: screening assessment can be used as day

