- 14. Lumbar puncture (T-ALL/T-LBL) for prophylactic intrathecal therapy: if prophylactic intrathecal therapy is foreseen by the treating physician, a lumbar puncture may be performed up to 3 days before the first dose of CB-103, and may be repeated at the discretion of the treating physician at the end of the first cycle and at the end of any subsequent cycles on or around day 28. If clinically feasible, one additional sample will be collected to determine the exposure of CB-103 in the CSF (this measurement will be done by a designated laboratory under Cellestia's responsibility).
- 15. For patients with PR or stable disease (SD) after the induction cycle(s) who may receive add-on selective therapy chosen by the investigator on the basis of the ongoing biomarker expression of the disease while continuing the treatment with the combination of CB-103 and venetoclax, the add-on therapy will be reported in details on the CRF.
- 16. EoT visit is to be done 5 days after the last dose of any study treatment, unless the patient starts any subsequent antitumor therapy (in which case the EoT visit should be performed before the start of the new therapy, whenever possible).
- 17 First follow-up visit will be 26 days after EoT (± 5 days), and every three months (± 14 days) thereafter, until EoS (i.e., death, patient's refusal, lost to follow-up) or study termination, whichever occurs first. Survival status and information on posterior antitumor therapies will be collected, telephone contact being acceptable.
- 18. If patient discontinued treatment without progression, tumor assessment will be done until progression or start of new antitumor treatment.
- 19. In case of relevant related toxicities (i.e., Grade>1), every 4 weeks until resolution or stabilization: information collected by telephone contact is acceptable.
- 20. Hepatitis B, C infection, and HIV will be obtained within 21 days of start of treatment.

Protocol 2021-0547 4/25/2024

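### After Cycle 1 Day 5 no scheduled ECG is required at CB-103 exposure, yet Section 7.2 lets torsades-risk drugs be used on the strength of a scheduled ECG

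*Combined protocol and SAP*

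**What the plan says.** **ECG schedule.** Section 8.7.1 sets ECGs at screening, Cycle 1 Day 1 and Cycle 1 Day 5, "and then at day 1 of all reinduction cycles and EOT". Timing relative to dose is given only for the two Cycle 1 visits, each with tracings 2 hours after the morning and evening doses. The EKG row of Table 16 agrees and has no mark on Day 26 of any cycle.

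**Timing rules.** Table 16 footnote 1 states: "Assessments scheduled on days of dosing should be done prior to administration of study drug(s), unless otherwise specified". Section 8 adds: "Assessments scheduled for days 1 of each cycle must be performed within 48 hours prior to study treatment administration". For end of treatment, footnote 16 says the "EoT visit is to be done 5 days after the last dose of any study treatment", or sooner if new therapy begins. Footnote 3 lets an assessment made on Days 26 to 29 count as the next Day 1.

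**Dosing.** Section 5.1.3 gives CB-103 as "500 mg twice a day (BID) for 5 days on and 2 days off". Patients enrolled before Version 2.0 may stay on 500 mg daily.

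**Rules that use ECGs.** Section 7.2 says that drugs with known or conditional torsades risk "should be strictly prohibited during the study treatment period, unless there are no signs of QTc prolongation in scheduled EKG". Table 12 withholds CB-103 in any cycle for QTcF of 480 ms or more on an ECG read by the Investigator. Footnote 6 covers unscheduled tracings: "these assessments may be repeated at the Investigator's discretion in case of signs or symptoms of cardiotoxicity". Section 6.1.5 describes intensive cardiac monitoring that includes Holter ECGs, but Section 8.7 and Table 16 schedule no Holter.

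**The concern.** The ECGs exist because Section 6.1.5 reports QT prolongation in non-clinical studies at higher CB-103 doses. A tracing taken before the first dose after a 2-day break is a poor test of that effect. The protocol handles the same timing correctly for pharmacodynamic blood: under Section 8.9.4, "blood samples must be taken on the last week-day of CB-103 intake before the 2 days off treatment". The ECG schedule has no such instruction.

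The rule most affected is Section 7.2. It does not say which scheduled ECG counts. During the rest of Cycle 1 the latest one is Cycle 1 Day 5, which is on drug. From Cycle 2 the latest one is normally a tracing taken in, or at the end of, the CB-103 break. A patient could be cleared on that tracing to start a torsades-risk drug and then take the two together with no ECG required until the next pre-dose Day 1.

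Such drugs are foreseeable. Table 4 lists fluconazole, ciprofloxacin, posaconazole and voriconazole as interacting with venetoclax. The first two are in Appendix 1 Table 1 (known risk) and the other two in Appendix 1 Table 2 (conditional risk). What is at stake is the safety of a patient who starts one of these after Cycle 1 Day 5.

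**Working it through.** The plan gives no figure to reproduce, so the check lays the dosing pattern over the calendar.

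**1. Dosing days.** Inputs: 28-day cycle (Section 4.1) and 5 on, 2 off (Section 5.1.3). CB-103 days are 1–5, 8–12, 15–19 and 22–26, or 20 per cycle. Day 26 is the last dosing day and Days 27–28 are off. Section 8.9.4 fits this: its Day 26 blood sample must fall on the last CB-103 day before the break.

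**2. Dosing days after the last required post-dose ECG (Cycle 1 Day 5).**
- Cycle 1: 20 − 5 = 15 of 20 (75%)
- Two cycles: 40 − 5 = 35 of 40 (88%)
- Five cycles: 100 − 5 = 95 of 100 (95%)

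From Day 5 to the next scheduled ECG (Day 29) is 24 days, or 21 if it is done on Day 26 under footnote 3.

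**3. Time since the last CB-103 dose.** Take the Day 26 morning dose as hour 0. Section 5.1.3 puts the evening dose 8 to 12 hours later. The Day 29 morning dose is at hour 72.
- Just before the Day 29 dose: 72 − 12 = 60 h to 72 − 8 = 64 h
- Earliest edge of the 48-hour window: 60 − 48 = 12 h to 64 − 48 = 16 h
- EOT at 5 days: 5 × 24 = 120 h
- Patients kept on 500 mg daily with no break: about 24 h, a trough

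**4. Drug remaining.** The documents give no CB-103 half-life, so these values are assumptions. Fraction remaining = 0.5^(t / half-life).

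| Assumed half-life | 12–16 h | 60–64 h | 120 h |
|---|---|---|---|
| 6 h | 16–25% | about 0.1% | <0.1% |
| 12 h | 40–50% | 2–3% | 0.1% |
| 24 h | 63–71% | 16–18% | 3% |
| 48 h | 79–84% | 40–42% | 18% |

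With a half-life up to 24 h, the usual Day 1 tracing sees less than a fifth of the level that followed the last dose.

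**5. Can other text supply an on-drug ECG?**
- Footnote 3 permits a Day 26 assessment, but the EKG row has no Day 26 mark, and footnote 1 would make such a tracing pre-dose by default.
- Footnote 6 needs a sign or symptom, and QTc prolongation can be silent.
- Table 12 raises ECG frequency, but only after a QTcF finding.
- The Holter ECGs in Section 6.1.5 have no scheduled time.

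None of these requires a tracing at CB-103 exposure after Cycle 1 Day 5.

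**The case against.** Front-loaded monitoring is a defensible choice. Cycle 1 Day 5 gives two post-dose tracings with venetoclax already at 400 mg. After 96 h of dosing, the fraction of steady state is 1 − 0.5^(96 / half-life): 94% at an assumed 24 h and 75% at 48 h. Reinduction uses the same dose, patients are admitted for Days 1–7, and Section 2.3.2 reports no QTc prolongation among 79 patients. All of this stands and limits the concern to what starts after Day 5.

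Section 5.2.2 also requires strong or moderate CYP3A inhibitors to be at steady state before venetoclax begins. A patient already on an azole is therefore tested on the whole combination at Cycle 1 Day 5. That stands too, but Table 3 has a column for co-administration after ramp-up, so later starts remain possible.

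The same text rules out several stronger readings that a reader might infer:

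- *Every later ECG is off CB-103.* Too absolute. Footnote 3 allows an on-drug Day 26 tracing, patients kept on 500 mg daily may have no break, and at 12 to 16 h the drug level may be close to an ordinary overnight trough.
- *Table 12 depends on the scheduled ECGs.* It does not. It acts on any ECG that the Investigator reads. The gap is that routine monitoring supplies none at CB-103 exposure.
- *Electrolyte shifts go unwatched.* They do not. Chemistry is at least twice weekly in Cycle 1 and weekly afterwards (Section 8.9.3), and the second footnote to Table 12 withholds CB-103 until low potassium or magnesium is corrected.
- *The efficacy and toxicity monitoring in Section 12 is compromised.* The documents give no rate of undetected, related, grade 3 or higher QTc events on Days 6–28, so no shift in the Table 19 figures can be supported.

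**Conclusion.** The point holds as a gap in safety monitoring. After Cycle 1 Day 5 no scheduled ECG is required at CB-103 exposure. The usual later tracing falls 60 to 64 hours after the last dose, and the EOT tracing about 120 hours after. Section 7.2 can still clear a known- or conditional-risk torsades drug on such a tracing, with no ECG required once that drug is started.

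The conclusion assumes the 5-on/2-off pattern starts on Day 1 and runs without interruption. It does not depend on a particular half-life, which only decides how little drug the Day 1 tracing sees. It concerns CB-103 alone, since venetoclax is continuous. It does not show that CB-103 prolongs QTc in patients, and it leaves the sample size, stopping boundaries and error rates untouched. It is a cheap improvement worth making.

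**What to change.** 1. **Section 8.7.1 and Table 16.** Move the Day 1 ECG of Cycle 2 onward to Day 26 of every cycle, including Cycle 1, taken 2 hours after the morning CB-103 dose. State the timing explicitly so that footnote 1 does not make it pre-dose. Keep a Day 1 ECG only when the next cycle starts after Day 29, the limit already in footnote 3. Leave the Cycle 1 Day 1, Cycle 1 Day 5 and EOT tracings as they are.
2. **Section 7.2.** Replace the reference to a scheduled EKG with an ECG taken 2 hours after a CB-103 dose, repeated within about 7 days of starting the QT-prolonging drug. The 7 days is a proposal; the documents give no figure.
3. **Section 6.1.5.** Make the text match this schedule, and either schedule the Holter ECGs or remove them.

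**Cost.** No new visit is needed, because Table 16 already has a Day 26 visit with examination, blood pressure, laboratory tests and biomarker blood. For c cycles, c Day 26 tracings replace c − 1 Day 1 tracings, so the net is one extra per patient, or 30 for 30 patients. Add one per newly started QT-prolonging drug and one per delayed cycle. Section 12 does not change.
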